7.6.3.2. Data Analysis

The digital pdf ECG data will be downloaded and provided to Masimo. Three independent board-certified cardiologists will be tasked with rhythm classification and [REDACTED]

7.7. Monitoring Plan

Oversight for this clinical trial is provided by the sponsor, investigators, and IRB.

As the sponsor of this clinical investigation, Masimo Corporation is required by 21 CFR Part 812, of the Food and Drug Administration regulations to monitor and oversee the progress of the investigation. The monitor(s) assigned by Masimo Corporation to this task will be trained on departmental Standard Operating Procedures (SOPs) on conduct and monitoring of sponsored studies.

CLINICAL INVESTIGATION PLAN

Study Title: Validation of the performance of the electrocardiogram (ECG) function of the Masimo INVSENSOR00057

In accordance with good clinical practices guidelines, there will be at least three scheduled monitoring visits to ensure overall regulatory compliance of the study:

- An initiation visit, prior to any subject enrollment to confirm site readiness, and to document training on the study protocol and procedures, and use of equipment,
- At least one monitoring visit during initial enrollment, and/or every 2-3 months thereafter.
- A final close out visit after the last subject had finished the study.

The monitor will contact and visit the investigator and will be allowed, on request, to have access to all source documents needed to verify the entries in the CRFs and other GCP-related documents (IRB approvals, IRB correspondences, and ICFs), provided that subject confidentiality is maintained in agreement with HIPAA regulations. The Investigator will provide the monitor access to all necessary records to ensure the integrity of the data (21 CFR 812).

It will be the monitor's responsibility to inspect the CRFs at regular intervals throughout the study, to verify the adherence to the CIP and the completeness, consistency and accuracy of the data being entered on them.

During each visit, the monitor will also verify adherence to the inclusion/exclusion criteria, and documentation of SAEs/SADEs and protocol deviations/violations and check the CRF against source documentation.

After each visit, the monitor will provide a monitoring letter to the Investigator within four weeks of visit completion. The monitoring letter will detail the findings and open action items observed during the visit. It is the responsibility of the PI and study coordinator(s) to respond to the findings of the monitoring letter and complete any open action items as soon as possible but no later than 60 days of receiving the monitoring letter. Any open action items not completed within the time allowed may be sufficient grounds for study site suspension or termination; it will be up to the sponsor to determine whether any incomplete action items are sufficient grounds for suspension or termination.

Depending on the quality of the data and/or changes to factors affecting subject safety, additional monitoring visits may be necessary at the sponsor's discretion.

8. STATISTICAL DESIGN AND ANALYSIS

The study objective is to evaluate the performance of the INVSENSOR00057 rhythm classification and waveform characteristics relative to a 12-lead ECG. The INVSENSOR00057 evaluates a 30 second duration, single lead, ECG waveform measurement. One of four possible outcomes for each measurement per Table 8a.

Outcome	Description
AFib	Waveform is classified as atrial fibrillation
NSR	Waveform is classified as Normal Sinus Rhythm
Inconclusive	INVSENSOR00057 cannot determine the rhythm classification
Noise	INVSENSOR00057 has determined that the waveform is too noisy and does not represent a physiological signal

CLINICAL INVESTIGATION PLAN

Study Title: Validation of the performance of the electrocardiogram (ECG) function of the Masimo INVSENSOR00057

Data from subjects where reference 12-lead ECG did not provide readable ECG waveforms (as assessed by medical personnel) will be excluded from the primary analysis.

[figure not shown]
8.1. Classification Accuracy Calculations

8.1.1. Data Analysis

Classification accuracy will be measured on all measurements where both the INVSENSOR00057 and the 12-lead reference ECG provided a classification of either AFib or NSR. (This incidence rate of Inconclusive and Noise outcomes on the INVSENSOR00057 will be evaluated separately.) Sensitivity is the probability that the diagnostic test is positive for the disease, given that the subject actually has AFib, while specificity is the probability that the diagnostic test is negative, given that the subject does not have AFib (or conversely, has NSR).

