7.5.3. Number of Subjects

7.5.4. Subject Classifications

Subjects will be classified according to the criteria below:

- **Screened** – Subjects who are assessed for study eligibility.
- **Enrolled** – Subjects who have met all the inclusion criteria, do not meet any exclusion criteria, and have been assigned a subject identification number.
- **Screen Failure** – Subjects who do not meet all the eligibility criteria. (Reason for the subject's ineligibility will be documented on a *Screening and Enrollment Log*).
- **Withdrawn** – Subjects who do not complete the study due to reasons listed below:
 - Subject voluntarily opts not to participate.
 - Subject was discontinued from study at the discretion of the clinical team.
- **Completed** – Subjects with a completed simultaneous ECG measurement using Masimo INVSENSOR00057 and interpretable 12-lead reference ECG.

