7.6. Study Procedures

7.6.1. Subject Recruitment and Pre-screening

Subjects with no known arrhythmia (normal sinus rhythm) will be recruited at [REDACTED] and subjects with known diagnosis of atrial fibrillation will be recruited at external sites from medical clinics or cardiology offices. Subjects in the AFib cohort may have paroxysmal, persistent, or permanent forms of AFib, and will be determined by the referring cardiologist to be in atrial fibrillation at the time of routine office visit.

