7.6.2. Informed Consent and Screening

Following the identification of a potential eligible subject as defined by the inclusion and exclusion criteria, the subject will be informed about the purpose of the study and given an overview of the study procedures. Study staff will explain the potential risks and benefits, and discuss the subject's rights and privacy information. Subjects will be provided with ample time to review the consent form and ask questions. The research team will emphasize that participation is voluntary and declining participation in the study will not result in any penalty or loss of benefits that the subject is otherwise entitled.

Once the subject's questions have been answered and the consent documents are signed and dated, the Principal Investigator or delegate will also sign the informed consent documents, approving the subject to be enrolled in the study. The investigator shall retain the original copy of the signed informed consent documents in each subject's records and provide a copy to the subject. No study related activities shall be conducted until the consent form is signed.

Study Title: Validation of the performance of the electrocardiogram (ECG) function of the Masimo INVSENSOR00057

Subjects will be screened to determine eligibility for study enrollment. Subjects must meet all inclusion criteria and none of the exclusion criteria to participate in the study. All subjects screened will be documented on the *Screening and Enrollment Log*. Subjects who do not meet the eligibility criteria will be considered screen failures and the reason for the status of screen failure will be documented on the *Screening and Enrollment Log*.

Information on subject demographics, medical history including comorbidities and concurrent medications will be collected (see [Appendix II](#)).

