7.6.3. Study Procedures

7.6.3.1. ECG Measurements

The Masimo INVSENSOR00057 placed on the wrist according to the *Investigator Brochure (IB)*. Site staff will check proper application of wrist strap. Next, the reference 12-lead ECG electrodes will be placed. INVSENSOR00057 will be paired via Bluetooth connection [REDACTED]

The subjects will be provided with assistance with INVSENSOR00057 placement according to the user manual [REDACTED] Once the subject is familiarized with the device, study measurement commences.

The on-site trained research personnel will confirm the ECG recordings are of diagnostic quality prior to removing the electrodes. At the conclusion of the procedure, the 12-lead ECG electrodes and INVSENSOR00057 will be removed.

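### Does the plan leave open whether a subject whose study 12-lead is read as a different rhythm from the one at enrolment stays in the accuracy analysis?

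*Combined protocol and SAP*

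**What the plan says.** **Entry and recruitment.** Section 7.5.1 defines Group 1 as people with no earlier arrhythmia diagnosis who present in NSR, and Group 2 as people with an AFib history who present in AFib. Section 7.6.2 adds: "Subjects must meet all inclusion criteria and none of the exclusion criteria to participate in the study". Under Section 7.6.1, AFib candidates "will be determined by the referring cardiologist to be in atrial fibrillation at the time of routine office visit".

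**Measurement and reading.** The on-site check visible in Section 7.6.3.1 concerns quality: "The on-site trained research personnel will confirm the ECG recordings are of diagnostic quality prior to removing the electrodes". Rhythm is read afterwards, under Section 7.6.3.2: "Three independent board-certified cardiologists will be tasked with rhythm classification". The rest of that sentence is redacted.

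**Subject statuses.** Section 7.5.4 defines Completed as "Subjects with a completed simultaneous ECG measurement using Masimo INVSENSOR00057 and interpretable 12-lead reference ECG" and Screen Failure as "Subjects who do not meet all the eligibility criteria". Neither definition mentions a mismatch found after measurement.

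**Analysis.** The synopsis (Groups and Randomization) and Section 7.1 both place subjects in rhythm cohorts by the clinical reading of the reference 12-lead, and Section 7.1 makes that reading the foundation of the endpoint analysis. Section 8.1.1 states that accuracy is "measured on all measurements where both the INVSENSOR00057 and the 12-lead reference ECG provided a classification of either AFib or NSR", with Inconclusive and Noise device outputs evaluated separately. The only other visible exclusion from the primary analysis, in the opening of Section 8, is an unreadable reference tracing.

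**The concern.** The order of steps allows a mismatch. A referring cardiologist judges AFib at an office visit, paroxysmal AFib is eligible, and three other cardiologists classify the study tracing later. A Group 2 subject could have returned to sinus rhythm by the time of the recording, or the readers could simply disagree with the referral.

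Such a subject matches neither group in Section 7.5.1 as the group is described, yet meets the definition of Completed and satisfies Section 8.1.1. If eligibility overrides the analysis rule, the subject leaves. If the analysis rule stands alone, the subject counts towards specificity. Were the plan really silent, the choice could be made after the device output was known, and specificity could move a little. A subject read as neither AFib nor NSR raises a smaller question: the visible text asks for no count of such subjects.

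**Working it through.** **1. Apply the analysis rule to each combination.** Assume a device output of AFib or NSR, as Section 8.1.1 requires.

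| Enrolled as | Study 12-lead read as | Place in the accuracy analysis | Source |
|---|---|---|---|
| Group 1 | NSR | specificity | 8.1.1 |
| Group 1 | AFib | sensitivity | 8.1.1, with 7.1 and synopsis |
| Group 2 | AFib | sensitivity | 8.1.1 |
| Group 2 | NSR | specificity | 8.1.1, with 7.1 and synopsis |
| Either | another rhythm | outside | 8.1.1 |
| Either | unreadable | outside | 8, opening text |

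Every row has an answer, and none depends on the enrolment label.

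**2. Check against eligibility.** Section 7.5.1 speaks of the rhythm at presentation, and Section 7.6.1 says who judges it for Group 2 and when. No visible sentence makes eligibility depend retrospectively on the later three-reader classification. Entry judged at presentation and analysis by the reference reading can both hold.

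**3. Is the rule sound?** Sensitivity and specificity condition on the true state when the test is taken, here the simultaneous reference tracing. A person with an AFib history who is in NSR during the recording is a genuine non-AFib case for that measurement. If the device errs more often in such people, keeping them lowers specificity, so the rule does not flatter the device.

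**4. Size.** The plan's sample size, expected accuracy and interval width are not visible, so there is no figure to reproduce. All counts below are assumptions. Let N be the Group 1 subjects, x of them called NSR; m the Group 2 subjects read as NSR; and c the AFib calls among those m.

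- Discordant subjects left out: x/N
- Discordant subjects kept: (x + m − c)/(N + m)

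With N = 150 and x = 147, leaving them out gives 147/150 = 98.0% (exact 95% CI 94.3 to 99.6). Keeping them gives:

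| m | c | Specificity | 95% CI |
|---|---|---|---|
| 3 | 0 | 150/153 = 98.0% | 94.4 to 99.6 |
| 3 | 1 | 149/153 = 97.4% | 93.4 to 99.3 |
| 8 | 0 | 155/158 = 98.1% | 94.6 to 99.6 |
| 8 | 1 | 154/158 = 97.5% | 93.6 to 99.3 |
| 8 | 3 | 152/158 = 96.2% | 91.9 to 98.6 |

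For m = 3 and c = 1, the shift is 100/103 − 98/100 = −0.9 points at N = 100, −0.6 at N = 150, and 198/203 − 196/200 = −0.5 at N = 200.

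The estimate falls only if c/m exceeds the 2% error rate assumed in Group 1. The falls shown use error rates of 1/3, 1/8 and 3/8, for which the documents give no support.

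A wider range uses 100 recruits per group and specificity 0.98 in Group 1. If 10% of AFib recruits are read as NSR, pooled specificity is (98 + 10s)/110, where s is specificity in those subjects. It runs from 0.964 at s = 0.80 to 0.980 at s = 0.98. At 20% discordance and s = 0.80 it is (98 + 16)/120 = 0.950.

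**5. Sensitivity.** Group 2 subjects read as NSR leave the sensitivity count under either treatment. A Group 1 subject read as AFib does depend on the treatment. From an assumed 147/150, adding one such subject gives 148/151 = 98.0% if detected and 147/151 = 97.4% if missed.

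**The case for a change.** The best case for a change is that eligibility and analysis are written on different bases. Section 7.5.1 requires both a history and a rhythm, Section 7.6.2 requires every criterion to be met, and no visible sentence says whether a failure discovered later removes the measurement. One careful reader may conclude that the subject is ineligible, another that the subject is included. The same membership affects the NSR cohort used for the heart-rate criterion in Section 8.3. A sentence or two would settle it at almost no cost.

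Part of this stands. Section 7.5.4 has no label for a subject found discordant after measurement, and no visible text asks for a count of discordant or third-rhythm readings. A good report would give both.

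The inference to an open analysis choice does not stand. Section 8.1.1 is categorical, and Section 7.1 ties the analysis to the reference reading. Dropping a readable AFib/NSR pair would depart from the stated rule; it would not be a use of discretion the plan leaves. The same reading settles the NSR cohort for heart rate. Eligibility errors also have a route outside the status list: monitors verify the entry criteria and the documentation of deviations (Section 7.7), and Section 11 governs reporting of deviations.

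Parts of Sections 7.1, 7.6.3 and 8 are redacted, and the Section 8 figure and the Appendix I workflow are not shown. A status rule may be there, so its absence from the visible text cannot be held against the plan.

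**Conclusion.** The concern does not call for a change. The visible plan analyses by the reference 12-lead reading, and following it as written gives a valid comparison with the reference standard. The residual gap is the administrative status of a discordant subject and a count in the report, which analysts can fill sensibly.

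The effect is nil if no reading differs from the enrolled rhythm, and nil for third-rhythm readings. For AFib-history subjects read as NSR, the assumed cases with 150 in Group 1 move specificity by between +0.1 and −1.8 points. A larger fall, to 95.0% from 98.0%, needs 20% discordance together with specificity of only 0.80 in those subjects. These sizes rest wholly on assumed counts. The conclusion itself rests on the wording of Sections 7.1 and 8.1.1 and the synopsis, and on hidden text not contradicting them.

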Groups and Randomization:	
Two groups of normal sinus rhythm and atrial fibrillation, where subjects are assigned to each group based on the clinical interpretation of the reference 12-lead ECG results. To ensure equal representation of two groups, a targeted enrollment approach will be taken at enrollment sites, where subjects with no known arrhythmia (normal sinus rhythm) will be recruited at Masimo Clinical Laboratory and subjects with known diagnosis of atrial fibrillation will be recruited at external sites.
 
• NSR - Subjects with no arrhythmia (normal sinus rhythm) based on the clinical interpretation of the reference 12-lead ECG results.• AFib - Subjects with known diagnosis of atrial fibrillation based on the clinical interpretation of the reference 12-lead ECG results.
Duration of the clinical investigation:	
The study is anticipated to require ~ 3 months to complete. Subject participation in the study will be approximately 30 minutes.

Study endpoint(s):	
Primary: Evaluate the diagnostic performance of ECG rhythm classification and waveform characteristics.
 
• Sensitivity and specificity of the automatic classification of atrial fibrillation (AFib) and normal sinus rhythm (NSR) by the single-lead ECG module of INVSENSOR00057 against clinical interpretation of a reference 12-lead ECG.• [REDACTED]• [REDACTED]• [REDACTED]

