3. DESCRIPTION OF THE STUDY DEVICE

As a leader in hospital pulse oximetry, Masimo brings over 30 years of innovation and breakthrough advances in noninvasive blood parameter monitoring to miniaturize its monitoring technology and integrate it into a wristwatch. Masimo INVSENSOR00057 [REDACTED] offers accurate, continuous health data and actionable health insights in a personal, lifestyle-friendly wristwatch. Masimo INVSENSOR00057 provides a variety of physiological data for consumers wanting to make better informed health and lifestyle decisions, improve their fitness, or track their health data. These parameters include hydration index (Hi), oxygen saturation level (SpO₂), pulse rate (PR), pulse rate variability (PRV), respiration rate (RRp[®]), pleth variability index (PVi), perfusion index (Pi). Additionally, Masimo INVSENSOR00057 is equipped with an ECG module, which captures the electrical signals of the heartbeat and informs user of potential atrial fibrillation (AFib) and their heart rate (HR). This validation study pertains to the ECG module of the Masimo INVSENSOR00057.

Study Title: Validation of the performance of the electrocardiogram (ECG) function of the Masimo INVSENSOR00057

As shown in Figure 1, the Masimo INVSENSOR00057 ECG

Figure 2).

A.

B.

Figure 1. Overview of Masimo INVSENSOR00057. A. Front and Back view of Masimo INVSENSOR00057 B. [REDACTED] Masimo INVSENSOR00057 can be paired with [REDACTED] devices to provide users with important health data.

With each ECG spot check, Masimo INVSENSOR00057 provides the average heart rate, rhythm classification, and a description of the classification as detailed below.

INVSENSOR00057 Rhythm Classification:

- Normal Sinus Rhythm

A Normal Sinus Rhythm ECG classification will indicate that ECG shows signs of a normal regular heartbeat with heart rates of 50 to 100 bpm. The ECG output of normal sinus rhythm only applies to the duration of the spot-check measurement and does not fully exclude cardiac arrhythmias. Subjects who are not feeling well should follow up with their healthcare provider.

- Atrial Fibrillation

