An atrial fibrillation ECG classification will indicate that ECG shows signs of irregular heartbeat. Atrial fibrillation is the most common pathologic cardiac arrhythmia. Masimo INVSENSOR00057 can detect signs of atrial fibrillation between heart rates of 50 to 150 bpm. Atrial fibrillation can often be accompanied by a rapid heart rate. Subjects who have not been previously diagnosed with atrial fibrillation and consistently receive this result or subjects who are not feeling well should consult with their healthcare provider. The resulting output does not guarantee the presence or absence of atrial fibrillation or other arrhythmias.

- Inconclusive

An Inconclusive ECG classification indicates that the ECG recording could not be classified, which may be due to a number of reasons such as other arrhythmias, pacing, or heart conditions that Masimo INVSENSOR00057

Study Title: Validation of the performance of the electrocardiogram (ECG) function of the Masimo INVSENSOR00057

is not designed to detect. It is recommended to repeat the measurement in a few minutes for subjects who get this result. An inconclusive classification does not indicate the presence or absence of any arrhythmias (including AFib) or other heart conditions. Subjects who consistently receive this result should follow up with their healthcare provider, particularly if they are feeling unwell.

- Noise

This classification of the ECG means the ECG waveform quality and performance were compromised and the device cannot report any measurements from the ECG.

INVSENSOR00057 Heart Rate Classification:

- Low Heart Rate

A low heart rate ECG classification will indicate a heart rate lower than 50 bpm, which can be commonly due to benign causes such as certain medication effects, or a normal finding during rest in particular among well-conditioned athletes or other cardiovascularly-fit individuals. However, subjects who are not feeling well should follow up with their healthcare provider as sometimes very low heart rates can indicate an underlying cardiovascular condition.

- High Heart Rate

A high heart rate ECG classification will indicate heart rates greater than 100 bpm, which can be due to exercise, stress, the presence of cardiac arrhythmia, or consumption of alcohol, stimulants or caffeinated drinks. Subjects who are not feeling well should follow up with their healthcare provider.

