8.3.2. Sample size

It is not possible to control the subject heart rate during this study, so it is not possible to validate the entire range of heart rate [REDACTED]. Further, the heart rate of Afib patients is ill defined, so a comparison in this cohort is not possible.

Therefore, the data collected in this study for the NSR cohort only will be used as a convenience sample of the INVSENSOR00057 heart rate output.

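### Does the primary specificity become ambiguous because reference NSR has no stated heart-rate limit?

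*Combined protocol and SAP*

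**What the plan says.** Section 8.1.1 (Data Analysis) states that "specificity is the probability that the diagnostic test is negative, given that the subject does not have AFib (or conversely, has NSR"). The analysis set is the measurements where "both the INVSENSOR00057 and the 12-lead reference ECG provided a classification of either AFib or NSR". Rates of Inconclusive and Noise outputs are evaluated separately.

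The reference group is defined in the Section 2 synopsis: "Subjects with no arrhythmia (normal sinus rhythm) based on the clinical interpretation of the reference 12-lead ECG results". Section 7.5.1 admits Group 1 subjects who present in normal sinus rhythm. Neither place gives a rate range. Section 7.6.3.2 assigns rhythm classification to three independent cardiologists, and the rest of that sentence is redacted.

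Rate limits appear only in the device description. In Section 3, the device's NSR result means a "normal regular heartbeat with heart rates of 50 to 100 bpm", and the device "can detect signs of atrial fibrillation between heart rates of 50 to 150 bpm". Under a separate heart-rate heading, "A high heart rate ECG classification will indicate heart rates greater than 100 bpm". Section 8 says "One of four possible outcomes for each measurement per Table 8a", and the table lists AFib, NSR, Inconclusive and Noise.

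Section 8.3.2 adds that "It is not possible to control the subject heart rate during this study", and Section 8.3.3 applies the heart-rate criterion over whatever range the NSR cohort shows.

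**The concern.** Section 8.1.1 treats not having AFib and having NSR as the same condition. They coincide only if every non-AFib reference reading is NSR. A reader who carries the 50 to 100 bpm range over to the reference could label sinus rhythm at 110 bpm as something else. The pair would then leave the analysis set, and no visible text reports it: the separate tally covers device outputs of Inconclusive and Noise, and the Section 8 exclusion covers unreadable reference ECGs. A reader who follows Section 2 would label it NSR, and an AFib output would be a false positive.

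This bears on a primary endpoint, and for such recordings the effect runs one way. If the device gives NSR only up to 100 bpm, a faster sinus recording can enter the specificity table only as a false positive, so leaving it out can raise specificity but not lower it. Heart rate is uncontrolled, so such recordings can occur, and the label is given after recording.

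**Working it through.** **Step 1: which recordings depend on the label.** Take a readable recording in sinus rhythm outside 50 to 100 bpm and apply the pair rule of Section 8.1.1.

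| Device output | Readers say NSR | Readers say something else |
|---|---|---|
| Inconclusive or Noise | dropped, counted in the separate rate | dropped, counted in the separate rate |
| NSR (conceivable just above 100 bpm) | true negative | dropped |
| AFib | false positive | dropped |

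The first row does not depend on the readers. The second hardly moves the estimate: from an assumed 147/150 = 98.00%, one added true negative gives 148/151 = 98.01%. Only the third row matters. Section 3 describes AFib output for 50 to 150 bpm, so below 50 bpm a false AFib call should not arise on the device's own description. What remains is an AFib output on sinus rhythm at about 101 to 150 bpm. Section 3 describes that output as a sign of irregular heartbeat; no visible passage suggests it is expected in regular sinus rhythm. Section 3 also does not state which rhythm class the device returns for sinus rhythm above 100 bpm, so the one-sided argument rests on an inference.

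**Step 2: the two supposed meanings of NSR.** Section 2 defines the reference group by absence of arrhythmia on clinical interpretation of the 12-lead ECG, and Section 7.5.1 is consistent with that. The 50 to 100 bpm range in Section 3 belongs to the device's output, and nothing visible tells the cardiologists to apply it. Low and High Heart Rate are listed in Section 3 as heart-rate classes, apart from the four rhythm classes. Those four are exactly the rows of Table 8a, so no rhythm outcome is left unmapped.

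**Step 3: size, as illustration only.** The sample size and its targets are redacted, so there is no plan figure to reproduce. Formula: specificity = TN/(TN + FP), with exact (Clopper-Pearson) two-sided 95% intervals. Assumptions: 150 reference-NSR pairs at 50 to 100 bpm, 3 of them called AFib, and k further AFib calls on faster sinus rhythm that readers label NSR.

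| k | Specificity | Lower 95% bound |
|---|---|---|
| 0 | 147/150 = 98.0% | 94.3% |
| 1 | 147/151 = 97.4% | 93.4% |
| 2 | 147/152 = 96.7% | 92.5% |
| 3 | 147/153 = 96.1% | 91.7% |
| 5 | 147/155 = 94.8% | 90.1% |

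If the readers did not label them NSR, the figure would stay at 98.0% throughout. With 100 to 300 pairs and 2% false calls, the gap runs from 0.3 points (one call among 300: 294/300 against 294/301) to 4.7 points (five among 100: 98/100 against 98/105).

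The same as shares: let t be the share of the cohort above 100 bpm and p the share of those called AFib, the rest not classified. Then S = 0.98(1 − t)/[(1 − t) + tp]. At t = 1%, p = 10%: 0.9702/0.991 = 97.9%. At t = 5%, p = 50%: 0.931/0.975 = 95.5%, a gap of 2.5 points. At p = 0 the gap is zero. The documents give neither t nor p.

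**Step 4: what a change would gain.** Rewording the condition as a reference reading of NSR is editorial, since the parenthesis already names NSR. Stating that reference NSR covers any sinus rate would repeat Section 2. A listing of readable reference ECGs read as neither rhythm would alter no estimate.

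**The case for a change.** The best argument for a change is that it would be cheap and would protect a primary endpoint. Three readers work independently, the label is given after recording, and a single recording can move the lower bound by about a point (94.3% to 93.4% above). The sample size rests on a confidence-interval method (Section 8.1.2), so the bound matters. The same gap covers any other readable non-AFib rhythm on the study recording, which the pair rule also drops without a visible report.

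Part of this stands. No visible passage gives a rate limit for reference NSR, and confirming one would cost little. But the argument needs readers to depart from the Section 2 definition, and it needs the device to call AFib on fast sinus rhythm; neither has support in the documents. The place where a reader rule would naturally sit, Section 7.6.3.2, breaks off in a redaction, and Section 8.2, much of Section 8.1.2 and the figure in Section 8 are not visible either. A rule that cannot be seen cannot be called absent.

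As for other rhythms, eligibility admits only subjects presenting in NSR or AFib, and the stated endpoint is AFib against NSR. Within that design, equating non-AFib with NSR is coherent. Nor is the direction fixed for such rhythms: three added with no AFib call, all counted as negatives, would give 150/153 = 98.04%, slightly higher than 98.0%.

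**Conclusion.** No change to the plan is called for. The missing rate limit is a detail that the Section 2 definition fills sensibly: sinus rhythm without arrhythmia is reference NSR at whatever rate, and an AFib output on it is a false positive. Nothing shows that following the plan as written would give a wrong specificity.

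The issue is confined to AFib outputs on sinus rhythm at about 101 to 150 bpm. Their number is unknown and may be zero. The illustrated loss of 0.3 to 4.7 points for one to five such calls among 100 to 300 subjects rests wholly on assumed counts. The conclusion assumes that the readers use NSR as Section 2 does and that no redacted passage says otherwise. A hidden rule imposing a rate limit on the reference label would need to be read before this view is final.
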